6.4 Analysis of Efficacy

Efficacy analyses of the primary and key secondary endpoints will be conducted on the ITT population. Other secondary efficacy analyses will be conducted on the mITT population.

For participants that switch from laparoscopic to open surgery during the surgical procedure, only Likert scale conspicuity assessments collected during the laparoscopic part will be used in the efficacy analysis.

6.4.1 Analysis of Primary Efficacy Endpoint

The primary efficacy endpoint is the investigator's blinded assessment of the intra-participant difference in ureter conspicuity for WL versus NIR-F at 30-min time point after ASP5354 administration based on a 5-point Likert scale.

6.4.1.1 Primary Analysis for Primary Efficacy Endpoint

The population used for the primary efficacy analysis will be the ITT population, which will include all adult normal/mild eGFR participants enrolled/randomized to the WL/NIR-F arm. Adolescents and moderate/severe eGFR participants that are enrolled directly into the WL/NIR-F arm will not be included in the primary analysis. All participants will have conspicuity scores from one ureter used in the analysis. The analysis ureter will be selected by the investigator using the procedure described in section 6.1. If the conspicuity assessment at the 30-min time point is missed for a participant in the adult normal/mild eGFR cohort, the first conspicuity assessment must be done while the investigator remains blinded to the participant's randomization assignment. The primary endpoint will be analyzed using a paired t-test. Prior to the analysis, data will first be imputed as follows if participants experience either ICE1 or ICE2:

- Participants who experience ICE1 will have both their NIR-F and WL conspicuity assessments at the 30-min time point after ASP5354 administration imputed as '1 = Not self-evident' for the primary endpoint analysis.
- Participants who experience ICE2 and do not have either a NIR-F or WL conspicuity assessment conducted at the 30-min time point after ASP5354 administration will have the first collected conspicuity assessment under the respective illumination mode used as

the 30-min time point value. If a participant does not have any assessments under a respective illumination mode during the entire surgery, the 30-min time point value will be set as the 30-min value from the other illumination mode. If a participant does not have any assessments under either illumination mode during the entire surgery, both 30-min time point values will be set as ‘1 = Not self-evident’.

Descriptive statistics will be used to summarize the ureter(s) conspicuity at the 30-min time point after ASP5354 administration with WL and the 30-min time point with NIR-F.

Descriptive statistics for the differences between the ureter(s) conspicuity scores and 95% 2-sided confidence interval for the mean difference and p-value will be presented.

All conspicuity Likert scale data will be listed.

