**Intercurrent Events (ICEs) and Strategies:**

*ICE1:* Participants who have received the medications or therapy listed below within 48 hours prior to ASP5354 administration and/or before the completion of the surgical procedure:

- ICG, unless used for anastomotic evaluation after the ureters have been visualized or for lymphatic mapping where there is a clear anatomic separation of the ureters and the lymphatics
- Other NIR-F imaging agents
- Ureteral stent

*Composite strategy for ICE1:* The assessment of ureter conspicuity after ICE1 will not be considered as relevant and will be handled as missing data. For participants that experience ICE1 prior to the 30-min time point conspicuity assessment by the investigator, both conspicuity values at the 30-min time point with WL and NIR-F will be set as '1 = Not self-evident' for the primary endpoint analysis.

*ICE2:* Participants who are unable to have ureter conspicuity assessed by the investigator at the 30-min time point for any reason.

*Treatment policy strategy for ICE2:* The assessment of ureter conspicuity in the event of ICE2 will be imputed as follows. In the event that WL or NIR-F conspicuity is not assessed by the investigator at the 30-min time point, the first collected conspicuity assessment under the respective illumination mode will be used as the 30-min time point value. If a participant does not have any assessments under a respective illumination mode during the entire surgery, the 30-min time point value will be set as the 30-min value from the other illumination mode. If a participant does not have any assessments under either illumination mode during the entire surgery, both 30-min time point values will be set as '1 = Not self-evident'.

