### **9.3.2 Primary Endpoint/Estimand(s) Analysis**

#### **9.3.2.1 Primary Analysis**

The primary efficacy endpoint is the investigator's blinded assessment of the intra-participant difference in ureter conspicuity for WL versus NIR-F at the 30-min time point after ASP5354 administration based on a 5-Point Likert scale. The population used for the primary efficacy analysis will be the ITT population, which includes all participants in the adult normal/mild eGFR cohort randomized to the WL/NIR-F arm. Adolescents and moderate/severe renally impaired participants that are enrolled directly into the WL/NIR-F arm will not be included in the primary analysis. The primary endpoint will be analyzed using a paired t-test.

Prior to the analysis, data will first be imputed as follows if participants experience either ICE1 or ICE2 (refer to primary estimands in [Section 3.1]):

- Participants who experience ICE1 will have both their NIR-F and WL conspicuity assessments at the 30-min time point after ASP5354 administration imputed as '1 = Not self-evident' for the primary endpoint analysis.
- Participants who experience ICE2 and do not have either a NIR-F or WL conspicuity assessment conducted at the 30-min time point after ASP5354 administration will have the first collected conspicuity assessment under the respective illumination mode used as

the 30-min time point value. If a participant does not have any assessments under a respective illumination mode during the entire surgery, the 30-min time point value will be set as the 30-min value from the other illumination mode. If a participant does not have any assessments under either illumination mode during the entire surgery, both 30-min time point values will be set as '1 = Not self-evident'.

Descriptive statistics will be used to summarize the ureter(s) conspicuity at the 30-min time point after ASP5354 administration with WL and the 30-min time point with NIR-F.

Descriptive statistics for the differences between the ureter(s) conspicuity scores and 95% 2-sided confidence interval for the mean difference and P value will be presented.

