5 ANALYSIS ENDPOINTS

5.1 Primary Efficacy Endpoint

The primary efficacy endpoint is the intra-participant difference in ureter conspicuity for WL versus NIR-F at the 30-min time point after ASP5354 administration. Conspicuity will be scored individually for each illumination mode using the 5-Point Likert Scale.

Primary Estimand

Population:

Male and female participants \geq 18 years of age and eGFR \geq 60 mL/min undergoing minimally invasive or open abdominopelvic surgeries. The population is further defined by the eligibility criteria.

Treatment Regimen:

The treatment regimen is ASP5354, 1 single dose of 3 mg.

Primary Endpoint:

Intra-participant difference in ureter conspicuity for WL versus NIR-F at the 30-min time point after ASP5354 administration. Conspicuity will be scored individually for each illumination mode using the 5-Point Likert Scale.

Intercurrent Events (ICEs) and Strategies:

ICE1: Participants who have received the medications or therapy listed below within 48 hours prior to ASP5354 administration and/or before the completion of the surgical procedure:

- Indocyanine green (ICG), unless used for anastomotic evaluation after the ureters have been visualized or for lymphatic mapping where there is a clear anatomic separation of the ureters and the lymphatics.
- Other NIR-F imaging agents
- Ureteral stent

Composite strategy for ICE1: The assessment of ureter conspicuity after ICE1 will not be considered as relevant and will be handled as missing data. For participants that experience ICE1 prior to the 30-min time point conspicuity assessment by the investigator, both conspicuity values at the 30-min time point under WL and NIR-F will be set as ‘1 = Not self-evident’ for the primary endpoint analysis.

ICE2: Participants who are unable to have ureter conspicuity assessed by the investigator at the 30-min time point for any reason.

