6.4.2 Analysis of Key Secondary Efficacy Endpoints

The population used for the analysis of key secondary endpoints will be the ITT population. Adolescent and moderate/severe renally impaired participants that are enrolled directly into the WL/NIR-F arm will not be included in the analysis of the key secondary endpoints.

The first key secondary endpoint of the 30-min time point WL conspicuity score versus the mean NIR-F conspicuity score across all time points will be analyzed using a sign test which will test if the median of the intra-participant time point difference means between the NIR-F score at each time point and the 30-min WL score is equal to 0. Prior to the analysis, the conspicuity scores will be windowed to time points every 30 minutes per the algorithm in Section 6.8.1.

The value used in the sign test for each participant will be derived as follows. The differences between the NIR-F scores at each time point and the 30-min WL score will be calculated for each participant. The mean of these differences will then be calculated for each participant. A sign test will be conducted using these mean differences to test if the median of the intra-

participant time point difference means between the NIR-F scores and 30-min WL scores is equal to 0.

Prior to the sign test, participants who experience ICE1 or ICE2 will have their 30-min conspicuity data imputed using the same algorithm as described in section [6.4.1.1](#).

Additionally, the following imputation rules will be applied to NIR-F conspicuity scores at other time points after 30-min prior to the sign test.

- Participants who experience ICE1 will have NIR-F conspicuity scores at time points after ICE1 set as their WL conspicuity assessment at the 30-min time point.
- Participants who are unable to have NIR-F conspicuity scores assessed by the investigator at time points after 30-min will have such NIR-F scores left as missing.

If a participant does not have a conspicuity assessment at a time point due to the surgery ending before the time point, the time point will be left as missing prior to the sign test.

The following results will be presented:

- For comparisons between WL and NIR-F:
 - Frequency and percentage of participants with a positive mean difference, negative mean difference and mean difference of 0.
 - Summary statistics of the mean differences between 30-min WL and NIR-F time points.

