The mean differences will be used to obtain a 2-sided p-value to test if the median of the mean differences is equal to 0.

[figure not shown]
The second key secondary endpoint of the 30-min time point WL conspicuity score vs the end of surgery NIR-F conspicuity score will be analyzed using a paired t-test.

Descriptive statistics will be used to summarize the ureter conspicuity at the 30-min time point with WL and the end of surgery (EoS) time point with NIR-F. The same imputation algorithm described in the analysis of the first key secondary endpoint will be applied to the data prior to setting the EoS NIR-F value for each participant. Descriptive statistics for the differences between the ureter conspicuity scores and 95% 2-sided confidence interval for the mean difference and p-value will be presented.

A fixed sequence testing procedure will be used to adjust for multiplicity and control the type I error rate. The hypothesis tests will be conducted in the following order.

- H1: WL conspicuity at 30 minutes vs NIR-F conspicuity at 30 minutes
- H2: WL conspicuity at 30 minutes vs mean NIR-F conspicuity across all time points
- H3: WL conspicuity at 30 minutes vs NIR-F conspicuity at end of surgery

H2 will only be tested if the H1 p-value is ≤ 0.05 . H3 will only be tested if both the H1 and H2 p-values are ≤ 0.05 . A graphical representation of the testing procedure is given below.

The values within the circles indicate the initial allocation of the 0.05 significance level. Therefore, at the initial test, the primary endpoint (H1) will be tested at the full significance level of 0.05 and the key secondary endpoints will not be tested. The values on the lines indicate the significance level from the prior step that is allocated to the next step if the null hypothesis is rejected. Therefore, if the null hypothesis for the primary endpoint is rejected, the first key secondary endpoint (H2) will be tested at the full significance level of 0.05. Subsequently, if the null hypothesis for the first key secondary endpoint is rejected, the second key secondary endpoint (H3) will be tested at the full significance level of 0.05.

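### The ICE1 imputation bullets leave out the estimand's timing condition, so taken alone they overwrite valid 30-minute scores of participants whose ICE1 came later

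*SAP*

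**What the plan says.** **Estimand.** Protocol 3.1 and SAP 5.1 attach a timing condition to the composite strategy for ICE1. In the SAP: "For participants that experience ICE1 prior to the 30-min time point conspicuity assessment by the investigator, both conspicuity values at the 30-min time point" are set to 1. The protocol uses the same condition: "For participants that experience ICE1 prior to the 30-min time point conspicuity assessment by the investigator".

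**Span of ICE1.** SAP 5.1 counts an event as ICE1 if it falls "within 48 hours prior to ASP5354 administration and/or before the completion of the surgical procedure". Protocol 6.8 allows stents during surgery on clinical judgement. ICE1 can therefore follow a completed 30-minute pair.

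**Primary analysis (H1).** SAP 6.4.1.1 states: "Participants who experience ICE1 will have both their NIR-F and WL conspicuity assessments at the 30-min time point after ASP5354 administration imputed as" 1, with no timing condition. Protocol 9.3.2.1 has the same bullet, but its lead-in points back to the estimand: "data will first be imputed as follows if participants experience either ICE1 or ICE2 (refer to primary estimands in [Section 3.1"). The SAP bullet has no such pointer.

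**Key secondary tests (H2, H3).** Protocol 9.3.3.1 repeats the bullet. SAP 6.4.2 imports it: "participants who experience ICE1 or ICE2 will have their 30-min conspicuity data imputed using the same algorithm as described in section" 6.4.1.1. It then adds a rule for later time points that is timed: "Participants who experience ICE1 will have NIR-F conspicuity scores at time points after ICE1 set as their WL conspicuity assessment" at 30 minutes. For H3: "The same imputation algorithm described in the analysis of the first key secondary endpoint will be applied to the data prior to setting" the end-of-surgery NIR-F value.

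**BICR.** SAP 6.4.3 applies the same ICE1 and ICE2 imputation to the BICR data.

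**The concern.** For a participant with a valid 30-minute pair and a later ICE1, the estimand keeps the pair and the bullet, taken alone, replaces it with 1 and 1. The section that defines the primary analysis is where a programmer looks for the rule, and the condition is missing there. Neighbouring rules (later NIR-F time points in SAP 6.4.2, CEF images in SAP 6.4.3) state their timing, so its absence from this bullet could be taken as deliberate.

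At stake are the 30-minute scores, including the blinded WL score, in all three tests of the fixed sequence. For H1 this conflicts with the stated estimand. For H2 and H3 it is inherited wording, because the documents define an estimand only for the primary endpoint. If the point stays open, the rule may be chosen once the affected participants are known.

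**Working it through.** **Inputs.** Protocol 9.5.1.1 and SAP 3 give a mean difference of 1.0, common SD 2.0, correlation 0.2, two-sided 0.05, paired t-test, 90% power and 84 randomized. The allocation ratio is not in the documents. The number of late ICE1 events is not given either.

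**The plan's own figure.** SD of the difference = √(2 × 2.0² × (1 − 0.2)) = 2.530. Noncentral-t power is 89.9% at n = 69 and 90.3% at n = 70. I assume n = 70 in WL/NIR-F, a 5:1 split of 84. A 4:1 split (67) gives 89.0% and a 6:1 split (72) gives 91.1%, so the stated 90% is reproduced.

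**H1.** Fix k of the 70 differences at 0. The expected mean becomes (70 − k)/70. Power by simulation, 1,000,000 runs for each k:

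| k (assumed) | expected mean | power |
|---|---|---|
| 0 | 1.000 | 90.3% |
| 1 | 0.986 | 89.9% |
| 3 | 0.957 | 89.0% |
| 5 | 0.929 | 88.1% |
| 10 | 0.857 | 85.3% |

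A noncentral-t calculation with the mixture mean and variance is close (84.8% at k = 10). The shift is towards zero.

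**Set-up for H2 and H3.** The 30-minute imputation is applied first, then the later-time-point rule. Two rules are compared: the bullet taken alone, and the bullet with the estimand's condition. They are run over all 25 combinations of WL 1–5 and constant NIR-F 1–5. A win is a positive difference (NIR-F minus WL), a loss a negative one.

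**H2, time points 30, 60, 90 and 120 minutes.**
- ICE1 between 90 and 120 minutes, WL 4, NIR-F 3. With the condition: (−1 −1 −1 + 0)/4 = −0.75. Bullet alone: WL and the 30-minute NIR-F become 1, the 60- and 90-minute NIR-F stay 3, the 120-minute NIR-F becomes 1, so (0 + 2 + 2 + 0)/4 = +1.0.
- Same timing, all 25 patterns: of 10 losses, 6 become wins and 4 become ties; of 5 ties, 4 become wins; all 10 wins stay wins. With WL at the floor of 1, no participant with ICE1 can be negative.
- ICE1 between 30 and 60 minutes: all 25 become ties, so 10 wins and 10 losses are lost.

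**H3.**
- ICE1 before the end-of-surgery NIR-F score: the difference is 0 under both rules in 25 of 25.
- ICE1 after an end-of-surgery score taken later than 30 minutes: the difference rises by (WL at 30 minutes − 1), that is 0 to +4. WL 4 with NIR-F 3 goes from −1 to +2.
- The 30-minute score is itself the end-of-surgery score: both values are overwritten and the difference is 0 in 25 of 25. WL 2 with NIR-F 4 goes from +2 to 0.

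These are counts of patterns, not probabilities.

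**The case against.** The strongest answer is SAP 6.8.1. It sends to the 6.4.1.1 algorithm only missing data and data that occur after ICE1. A 30-minute score taken before ICE1 is neither, so on this text it never reaches the bullet. SAP 6.8 likewise limits imputation to data affected by ICE1 or ICE2, and the protocol lead-in refers to Section 3.1. The later-time-point rule in SAP 6.4.2 points the same way: its reference to the 30-minute WL score would be an odd way to write 1. This stands. A reader might infer that the plan intends to overwrite every ICE1 participant, but the documents taken together do not support that. What remains is that SAP 6.4.1.1 does not say so itself.

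Late ICE1 should also be uncommon. Anticipated stenting is an exclusion criterion, and other NIR-F agents and most ICG use are not allowed through surgery. Ten cases would be 14% of the assumed arm. The sign reversals towards NIR-F need WL at or above NIR-F, against a planned advantage of 1.0 for NIR-F. This stands too.

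Finally, affected data would be visible: SAP 6.4.5 plans an ICE table and listing, a swimmer plot and summaries without imputation. SAP 6.4.1.2 repeats the primary test with affected assessments left missing. These help, but they do not settle the rule. The repeat test covers H1 only, and what counts as affected by ICE1 depends on the same unstated timing. No sensitivity test is planned for H2 or H3.

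**Conclusion.** The inconsistency is real and should be corrected. It rests on the text alone: the estimand has a timing condition, three bullets lack it, and ICE1 can occur after the 30-minute pair. The restricted rule is very probably what is meant.

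The effect is probably small. It is nil if no participant has a late ICE1. For H1 it is conservative, about 0.4 to 1.3 percentage points of power for one to three cases; this depends on the assumed n = 70 and the assumed counts. For H2 and H3 the direction is mixed. Setting WL to 1 while keeping NIR-F scores taken after 30 minutes and before ICE1 can favour NIR-F, whereas an ICE1 soon after 30 minutes (H2), or a 30-minute score that is also the end-of-surgery score (H3), removes wins as well as losses.

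A reader might conclude that the key secondary results are biased towards NIR-F, or that H2 and H3 contradict their own estimand. Neither follows: no ICE1 rate is given, the pattern counts carry no probabilities, and no estimand is stated for those endpoints.

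**What to change.** Before database lock, in SAP 6.4.1.1:

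1. Limit the ICE1 bullet with the clause already in the estimand: "For participants that experience ICE1 prior to the 30-min time point conspicuity assessment by the investigator".
2. Add that, for a later ICE1, the 30-minute WL and NIR-F analysis values are kept, whether observed or assigned under the ICE2 rule, and only NIR-F scores after ICE1 are set to the 30-minute WL analysis value, as SAP 6.4.2 already provides. Referring to the analysis value matters: a participant first assessed after the window, with ICE1 later still, has no observed 30-minute WL score.
3. State how ICE1 between the 30-minute WL and NIR-F readings is handled. WL always comes first, so this gap exists.

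The bullets in protocol 9.3.2.1 and 9.3.3.1 can be aligned at the next amendment. SAP 6.4.2 and 6.8.1 already carry timing language and need no other change. The BICR analysis follows the same rule.

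The cost is a few sentences in the SAP and a matching line in the programming specification. No new data are needed and the sample size is unaffected.

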6.4.1.2 Sensitivity Analyses for Primary Efficacy Endpoint

To examine the impact of out-of-window 30-min conspicuity assessments, the same paired t-test- as the primary analysis will be run with assessments impacted by ICE1 or ICE2 left as missing.

The difference in the ureter conspicuity at the 30-min time point post-ASP5354 administration between NIR-F and WL will be evaluated using a Wilcoxon signed-rank test. The p-value will be presented. Descriptive statistics for the WL and NIR-F conspicuity scores at the 30-min time point will also be presented. The Wilcoxon signed-rank test will be conducted using the same data (with ICE1 and ICE2 imputation) as the primary analysis.

To examine the impact of participants who are randomized but do not receive study drug, the primary analysis will be repeated excluding participants who are randomized to the WL/NIR-F arm but do not receive study drug.

Sensitivity analyses will be conducted on the ITT population.

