### **9.3.2.2 Sensitivity Analysis**

A sensitivity analysis for the primary endpoint will be conducted. The same paired t-test as the primary analysis will be run with the assessments impacted by ICE1 or ICE2 left as missing.

An additional sensitivity analysis for the primary endpoint will be conducted. The NIR-F and WL conspicuity assessments at the 30-min time point after ASP5354 administration will be compared using a Wilcoxon signed-rank test. This analysis will be conducted using the same data (with ICE1 and ICE2 imputation) as the primary analysis.

Sensitivity analyses will be conducted on the ITT population.

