Treatment policy strategy for ICE2: The assessment of ureter conspicuity in the event of ICE2 will be imputed as follows. In the event that WL or NIR-F conspicuity is not assessed by the investigator at the 30-min time point, the first collected conspicuity assessment under the respective illumination mode will be used as the 30-min time point value. If a participant does not have any assessments under a respective illumination mode during the entire surgery, the 30-min time point value will be set as the 30-min value from the other illumination mode. If a participant does not have any assessments under either illumination mode during the entire surgery, both 30-min time point values will be set as ‘1 = Not self-evident’.

Population Level Summary:

For participants randomized to WL/NIR-F, the score of the ureter conspicuity at the 30-min time point based on the 5-Point Likert Scale with NIR-F will be compared with the score of the ureter conspicuity at the 30-min time point based on the 5-Point Likert Scale with WL using absolute difference.

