 - ICG unless used for anastomotic evaluation after the ureters have been visualized or for lymphatic mapping where there is a clear anatomic separation of the ureters and lymphatics
 - Other NIR-F imaging agents
 - Ureteral stent
- ICE2 Total
 - ICE2, first conspicuity assessments collected after 30-min window
 - ICE2, first conspicuity assessment collected in 30-min window but either WL or NIR-F not collected
 - ICE2, no conspicuity assessments collected

A listing of ICEs will be provided. And a swimmer plot displaying NIR-F conspicuity scores for the index ureter and assessments impacted by ICEs for each patient will be provided.

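### The sensitivity analysis labelled as a check on out-of-window 30-min readings also removes imputed zero differences, so its contrast with the primary analysis can mask or mimic a late-reading effect

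*SAP*

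**What the plan says.** SAP 6.4.1.2 opens the first sensitivity analysis with its aim, "To examine the impact of out-of-window 30-min conspicuity assessments", and then says that the primary paired t-test "will be run with assessments impacted by ICE1 or ICE2 left as missing". SAP 6.8.1 supports the reading that late assessments are the target: for this analysis, a late assessment that the primary analysis would carry to 30 min is not mapped there. Protocol 9.3.2.2 specifies the same test, which "will be run with the assessments impacted by ICE1 or ICE2 left as missing", but attaches no out-of-window purpose to it.

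The two event types cover more than timing. ICE1 is use of ICG (with exceptions), another NIR-F agent or a ureteral stent. ICE2 is "Participants who are unable to have ureter conspicuity assessed by the investigator at the 30-min time point for any reason" (SAP 5.1). The primary analysis handles the resulting cases in two ways:

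- **Late first reading:** "the first collected conspicuity assessment under the respective illumination mode will be used as the 30-min time point value", so an observed score is used.
- **All others:** SAP 6.4.1.1 states that "Participants who experience ICE1 will have both their NIR-F and WL conspicuity assessments at the 30-min time point after ASP5354 administration imputed as" a score of 1. A participant never assessed also gets 1 in both modes. A mode never assessed takes the other mode's 30-min value. Each of these gives a difference of exactly 0.

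SAP 6.4.5 tabulates the ICE2 types separately, the first being "ICE2, first conspicuity assessments collected after 30-min window", but only for counts and a listing.

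**The concern.** A sensitivity analysis is read by comparing it with the primary result. Here a reader will take any shift, or the lack of one, as the effect of late readings, because that is the purpose the SAP states. Yet removing zeros raises a positive mean whatever the late readings do. If late readings show a larger gain than in-window ones, the two changes pull in opposite directions and the comparison can look reassuring. If late readings behave exactly like in-window ones, the comparison still moves.

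No other planned test fills the gap. The Wilcoxon signed-rank analysis keeps every imputation, and the third analysis in SAP 6.4.1.2 excludes only participants randomized but not dosed. What is at stake is the interpretation of one supporting analysis, not the primary hypothesis test.

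**Working it through.** **Background figure.** SAP 3 assumes a difference of 1.0, a common SD of 2.0 and a correlation of 0.2. The SD of the difference is √(2 × 2.0² × (1 − 0.2)) = √6.4 = 2.530. The exact paired t-test at 2-sided 0.05 has 89.9% power with 69 participants and 90.3% with 70. The stated 90% from 84 randomized therefore fits 5:1 allocation (70 of 84). It cannot be confirmed, because the ratio is held in a separate document. Nothing here disputes that figure; it only supplies N = 70 as a working assumption.

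**Notation.** N is the ITT size. k is the number of pairs containing a late reading, with mean difference dL. m is the number of pairs set to 0 by imputation. d is the mean difference of in-window pairs. d = 1.0 follows the plan's assumed difference; k, m and dL are assumptions.

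- Primary mean = [(N − k − m)d + k·dL] / N
- Planned sensitivity mean = d
- Primary minus planned = k(dL − d)/N − m·d/N
- Mean with only late pairs deleted = (N − k − m)d / (N − k)

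The first term of the contrast is the timing effect with everyone else held fixed. The second has nothing to do with timing. They cancel when k(dL − d) = m·d.

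| k | m | dL | Primary | Planned | Contrast | Timing term | Zero term | Late-only deletion |
|---|---|---|---|---|---|---|---|---|
| 8 | 7 | 2.0 | 1.014 | 1.000 | +0.014 | +0.114 | −0.100 | 0.887 |
| 7 | 7 | 2.0 | 1.000 | 1.000 | 0.000 | +0.100 | −0.100 | 0.889 |
| 14 | 7 | 1.5 | 1.000 | 1.000 | 0.000 | +0.100 | −0.100 | 0.875 |
| 8 | 7 | 1.0 | 0.900 | 1.000 | −0.100 | 0.000 | −0.100 | 0.887 |
| 0 | 7 | n/a | 0.900 | 1.000 | −0.100 | 0.000 | −0.100 | 0.900 |
| 7 | 7 | 0.5 | 0.850 | 1.000 | −0.150 | −0.050 | −0.100 | 0.889 |
| 7 | 0 | 2.0 | 1.100 | 1.000 | +0.100 | +0.100 | 0.000 | 1.000 |

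First row: primary = (55 × 1.0 + 8 × 2.0 + 7 × 0)/70 = 71/70 = 1.014, and late-only deletion = 55/62 = 0.887.

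Rows 1 to 3 show masking, complete in rows 2 and 3. Rows 4 and 5 show a shift with no timing effect. Row 6 shows overstatement. Row 7 shows that with no imputed zeros the planned analysis isolates late readings.

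**Limit of late-only deletion.** In row 4 late readings match in-window ones, yet deleting them moves the mean from 0.900 to 0.887. The zeros' weight rises from 7/70 to 7/62. That residual of 0.013 is much smaller than 0.100 but is not nil.

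**The case against.** The strongest reply is that the rule is sound and only the lead-in sentence is wrong. Protocol 9.3.2.2 presents the test as a general check on ICE handling, and it does answer whether the effect holds among pairs that neither event touches. That stands, and it is why the analysis should be kept. It does not rescue the SAP's stated purpose.

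A second reply is that late readings stay visible. SAP 6.4.5 gives ICE counts by type, a listing, a swimmer plot and unimputed scores by time point, and SAP 6.5.6 summarizes time from dosing to first assessment. These are useful, but none estimates the effect of late readings on the mean difference.

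A third reply is size. With an SD of 2.530 and N = 70 the standard error is about 0.302, so a zero term of 0.100 is a third of it. That is fair, and the illustrated counts are assumed.

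Stronger readings are tempting but unsupported:

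- A reader might infer that the analysis will hide a late-reading effect. Full masking needs both imputed zeros and late gains larger than in-window gains.
- A reader might take the gap between 1.014 and 0.887 (0.127) in the first row as the timing effect. It is a deletion effect; the timing term is 8 × (2.0 − 1.0)/70 = 0.114.
- A reader might infer that the first ICE2 subcategory captures every late reading. The second covers a first assessment in window with one mode not collected there, and that mode may first be read late.
- A reader might infer that every ICE1 participant is removed. SAP 5.1 limits the imputation to ICE1 before the 30-min assessment, whereas SAP 6.4.1.1 states no such limit. The point stands on either reading, for whichever participants are set to zero.

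**Conclusion.** The stated purpose and the rule in SAP 6.4.1.2 do not match. When the primary analysis contains imputed zeros, the contrast with this analysis combines a late-reading effect with removal of those zeros, and it can mask, mimic or overstate the former. When there are none, it isolates late readings correctly. At N = 70 and d = 1.0, each imputed zero contributes 1.0/70, about 0.014. The actual size depends on ICE counts and late-reading gains that the documents do not give.

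The primary analysis and the H1 to H3 testing sequence are unaffected. A reader might infer that the primary result is biased by this; nothing in the point bears on that. It is a modest defect in a supporting analysis, worth correcting because the correction is cheap.

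**What to change.** In SAP 6.4.1.2:

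1. Keep the present paired t-test, but relabel it as the effect of all ICE1 and ICE2 handling, consistent with Protocol 9.3.2.2.
2. Add one paired t-test that sets to missing only the pairs in which a WL or NIR-F value carried to 30 min was first collected after the 30-min window of SAP 6.8.1. Identify them from the recorded assessment times: all of the first ICE2 subcategory in SAP 6.4.5, plus those in the second whose other mode was read late. Keep all other primary-analysis imputations.
3. Because late-only deletion slightly re-weights the imputed zeros, show the mean difference for in-window pairs and for late pairs side by side, with counts.

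State also where a participant with one mode read late and the other never read is counted, since that difference is zero by imputation whatever the timing.

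The data are already collected, so the cost is SAP wording and one more table. SAP 1 allows updates before database lock; after lock, the added analysis should be documented in the clinical study report.
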